## Guidance documents

This statistical analysis plan is designed to comply with the standards issued by the International Council for Harmonisation of Technical Requirements for Pharmaceuticals for Human Use (ICH) E3 Structure and Content of Clinical Study Reports, E6 Good Clinical Practice, E9 Statistical Principles for Clinical Trials, and E9(R1) Addendum on Estimands and Sensitivity Analysis in Clinical Trials.

THIS DOCUMENT CONTAINS CONFIDENTIAL INFORMATION AND MUST NOT BE COPIED OR MADE AVAILABLE TO ANY THIRD PARTY WITHOUT THE PRIOR WRITTEN CONSENT OF THE LEO PHARMA GROUP

## List of abbreviations

AE	adverse event
AESI	adverse event of special interest
AD	atopic dermatitis
ADA	anti-drug antibodies
ADaM	Analysis Data Model
ADRG	analysis data reviewer's guide
ASDD	analysis set definition document
ATC	Anatomic Therapeutic Chemical Classification
BSA	body surface area
CDISC	Clinical Data Interchange Standards Consortium
CDLQI	Children's Dermatology Life Quality Index
CI	confidence interval
COVID-19	coronavirus disease 2019
CTP	clinical trial protocol
CTR	clinical trial report
DBL	database lock
Define.xml	data definition document
DLQI	Dermatology Life Quality Index
EASI	Eczema Area and Severity Index
EASI75	at least 75% reduction in EASI score from baseline
EASI50	at least 50% reduction in EASI score from baseline
EASI90	at least 90% reduction in EASI score from baseline
eCRF	electronic case report form
EMA	European Medicines Agency
ePRO	electronic patient-reported outcome
FAS	full analysis set
FDA	United States Food and Drug Administration
GCP	Good Clinical Practice
ICH	International Council for Harmonisation of Technical Requirements for Pharmaceuticals for Human Use
IGA	investigator's Global Assessment
IMP	investigational medicinal product

THIS DOCUMENT CONTAINS CONFIDENTIAL INFORMATION AND MUST NOT BE COPIED OR MADE AVAILABLE TO ANY THIRD PARTY WITHOUT THE PRIOR WRITTEN CONSENT OF THE LEO PHARMA GROUP

ISR	injection site reaction
MedDRA	Medical Dictionary for Regulatory Activities
nAb	neutralising antibodies
PCR	polymerase chain reaction
PK	pharmacokinetic(s)
POEM	Patient-Oriented Eczema Measure
PRO	patient-reported outcome
PT	preferred term
PYE	patient years of exposure
Q2W	every other week
SAE	serious adverse event
SAF	safety analysis set
SAS	Statistical Analysis Software
SC	subcutaneous(ly)
SD	standard deviation
SFU	safety follow-up
SOC	system organ class

THIS DOCUMENT CONTAINS CONFIDENTIAL INFORMATION AND MUST NOT BE COPIED OR MADE AVAILABLE TO ANY THIRD PARTY WITHOUT THE PRIOR WRITTEN CONSENT OF THE LEO PHARMA GROUP

## Version history

The statistical analysis plan (SAP) for trial LP0162-1338 is based on the clinical trial protocol (CTP) version 3.0 dated 24-Aug-2022.

SAP version	Date	Change	Rationale
1.0	13-Feb-2023	Not applicable	Original version
2.0	26-Apr-2023	Include entire trial period for all adult subjects in the interim analysis	Scope of interim analysis changed

THIS DOCUMENT CONTAINS CONFIDENTIAL INFORMATION AND MUST NOT BE COPIED OR MADE AVAILABLE TO ANY THIRD PARTY WITHOUT THE PRIOR WRITTEN CONSENT OF THE LEO PHARMA GROUP

## 1 Introduction

The statistical analysis will be performed as outlined in the CTP version 3.0. This SAP, prepared before database lock, supplements the CTP, and contains a more technical and detailed elaboration of topics related to the specification and implementation of the statistical analysis described in the CTP. The level of detail should enable the reader to reproduce all statistical analyses described in the SAP and the CTP.

Changes to the protocol-planned analyses are described/summarised in Section 6, while supplementary analysis specifications are elaborated in the individual sections.

Data handling decisions and derivation rules used in the analysis datasets are specified in the analysis data reviewer's guide (ADRG) and Data Definition document (define.xml).

THIS DOCUMENT CONTAINS CONFIDENTIAL INFORMATION AND MUST NOT BE COPIED OR MADE AVAILABLE TO ANY THIRD PARTY WITHOUT THE PRIOR WRITTEN CONSENT OF THE LEO PHARMA GROUP

## 1.1 Trial objectives, estimands, and endpoints

Objectives	Endpoints
Primary objective	Primary endpoints 
 
IGA score of 0 (clear) or 1 (almost clear) at Week 16.
 
EASI75 at Week 16.
 

Secondary objective	Secondary endpoints 
 
Number of treatment-emergent AEs from baseline to Week 16.
 
Presence of treatment-emergent ADA from baseline to Week 16.
 

Other objectives	Other endpoints 
 
Successful IMP self-administration when observed at the clinic at Week 4.
 
Successful IMP self-administration when administered at home at Week 8.
 

To evaluate the efficacy of tralokinumab administered by an autoinjector on severity and extent of AD, itch, and HRQoL in treating moderate-to-severe AD.	Other endpoints 
 
EASI90 at Week 16.
 
EASI50 at Week 16.
 
Percentage change in EASI score from baseline to Week 16.
 
Change in POEM from baseline to Week 16.
 
Reduction in POEM of at least 4 from baseline to Week 16/Reduction in POEM of at least 6 from baseline to Week 16.
 
Change in DLQI/CDLQI from baseline to Week 16.
 
Reduction in DLQI of at least 4 from baseline to Week 16/Reduction in CDLQI of at least 6 from baseline to Week 16.
 
Change in Eczema-related Weekly Sleep NRS from baseline to Week 16.
 
Change in Worst Weekly Pruritus NRS/Adolescent's Pruritus NRS from baseline to Week 16.
 
Reduction of Worst Weekly Pruritus NRS/Adolescent's Pruritus NRS of at least 4 from baseline to Week 16.
 

- Only adult subjects with a score of 4 and above and adolescent subjects with a score of 6 and above at baseline will be included in the analysis.
- For adult subjects, a response is defined as a reduction of at least 4 from baseline. For adolescent subjects, a response is defined as a reduction of at least 6 from baseline.
- Only subjects with Worst Weekly Pruritus NRS/Adolescent's Pruritus NRS score of 4 or above at baseline will be included in the analyses.

**Abbreviations:** AD = atopic dermatitis; ADA = anti-drug antibodies; AEs = adverse events; CDLQI = Children's Dermatology Life Quality Index; DLQI = Dermatology Life Quality Index; EASI = Eczema Area and Severity Index; EASI90/EASI75/EASI50 = at least 90% / 75% / 50% reduction in EASI score; HRQoL = health-related quality of life; IGA = Investigator's Global Assessment; IMP = investigational medicinal product; NRS = numeric rating scale; POEM = Patient-Oriented Eczema Measure.

THIS DOCUMENT CONTAINS CONFIDENTIAL INFORMATION AND MUST NOT BE COPIED OR MADE AVAILABLE TO ANY THIRD PARTY WITHOUT THE PRIOR WRITTEN CONSENT OF THE LEO PHARMA GROUP

The primary endpoints will be analysed using a composite estimand strategy to handle the occurrence of two intercurrent events considered to affect the interpretation of the estimates of the endpoints (initiation of rescue medication and permanent discontinuation of IMP).

The composite estimand evaluates the response rate without initiation of rescue treatment or permanent discontinuation of IMP. For subjects who received rescue treatment prior to Week 16 or who have permanently discontinued IMP prior to Week 16, observed data after the intercurrent events will be considered non-response, reflecting an assumption that initiation of rescue treatment or permanent discontinuation of IMP indicates either failure of the treatment to achieve response or that a possible positive response is not attributable to the treatment alone. Missing data for subjects who do not attend the Week 16 visit and where rescue medication has not been used, nor the subject has permanently discontinued IMP, will be imputed as non-response.

## 1.2 Trial design

This is an open-label, single-arm, phase 3 trial, in adult and adolescent (age 12 to 17 years) subjects with moderate-to-severe AD. The trial is designed to evaluate the efficacy and safety of tralokinumab administered by an autoinjector. The trial design is illustrated in [Panel 1](#).

The trial will consist of a 2- to 4-week screening period, a 16-week treatment period, and a 4-week safety follow-up period.

[figure not shown]
Approximately 130 subjects, of which approximately 30 subjects will be adolescents are planned to be assigned to the treatment. The trial will be conducted at approximately 30 sites in US. The anticipated average number of subjects assigned to treatment per trial site is 4.

For details on trial design, see Section 7 of the CTP.

THIS DOCUMENT CONTAINS CONFIDENTIAL INFORMATION AND MUST NOT BE COPIED OR MADE AVAILABLE TO ANY THIRD PARTY WITHOUT THE PRIOR WRITTEN CONSENT OF THE LEO PHARMA GROUP

## Panel 1: Trial design

Approximately 130 subjects, of which approximately 30 subjects will be adolescents are planned to be assigned to the treatment.

**Abbreviations:** IMP = investigational medicinal product; Q2W = every other week; w = weeks.

An interim CTR including only adult subjects will be made to support submission for marketing approval of tralokinumab. The interim analysis will be based on data collected for adult subjects during the trial period and performed after interim database lock (DBL).

The primary analysis based on 100% data availability and all subjects (adults and adolescents) will be performed after DBL.

## 2 Testing strategy

There will be no formal testing.

## 3 Sample size

Sample size documentation is provided in the CTP Section 14.1.

Approximately 130 subjects of whom approximately 30 are adolescents, will be assigned to treatment.

THIS DOCUMENT CONTAINS CONFIDENTIAL INFORMATION AND MUST NOT BE COPIED OR MADE AVAILABLE TO ANY THIRD PARTY WITHOUT THE PRIOR WRITTEN CONSENT OF THE LEO PHARMA GROUP

## 4 Trial analysis sets

All screened subjects will be accounted for in the CTR.

All subjects assigned to treatment and who received at least 1 dose of IMP will be included in the full analysis set (FAS) and the safety analysis set (SAF). Exclusions from the FAS can be considered in special cases as described in ICH E9, Section 5.2.1., Full Analysis Set. If it is decided to exclude a subject who has received IMP from the FAS, a justification addressing ICH E9 will be given.

The decisions regarding inclusion/exclusion of subjects or subject data from the trial analysis sets will be documented in the analysis set definition document ASDD (TMF-000811745).

For the purposes of analysis, the definition of the analysis sets are listed in [Panel 2](#).

### Panel 2: Trial analysis sets

Trial analysis set	Description and purpose
Full analysis set (FAS)	
 
• All subjects assigned to treatment and who received at least 1 dose of IMP.
 
• The FAS is used to analyse endpoints related to the efficacy objectives
 

Safety analysis set (SAF)	
 
• All subjects assigned to treatment and who received at least 1 dose of IMP.
 
• The SAF is used to analyse the endpoints and assessments related to safety, PK and ADA during the treatment period.
 

Usability analysis set	
 
• All subjects assigned to treatment, who received at least 1 dose of IMP and have been trained in the usage of the autoinjector by investigator or delegated staff at the baseline visit.
 
• Usability analysis set will be used to analyse objectives related to subject self-administration.
 

Safety follow-up (SFU) analysis set	
 
• All subjects for whom date of last contact is after the date of exposure end, where exposure end is defined as the date of week 16 visit for subjects completing the treatment period, and otherwise the date of permanent discontinuation of IMP for subjects not completing the treatment period.
 
• SFU analysis set is used to analyse endpoints and assessments related to safety during the SFU period.
 

**Abbreviations:** IMP = investigational medicinal product

THIS DOCUMENT CONTAINS CONFIDENTIAL INFORMATION AND MUST NOT BE COPIED OR MADE AVAILABLE TO ANY THIRD PARTY WITHOUT THE PRIOR WRITTEN CONSENT OF THE LEO PHARMA GROUP

## 5 Statistical analysis

### 5.1 General principles

The first day of dosing is considered baseline (Week 0, Visit 2).

All CIs will be presented with 95% degree of confidence, unless otherwise specified. The Wilson method is used to calculate the CI for the binary endpoints, and the statistically method Student's t-CI is used to calculate the CI for the continuous endpoints.

An observed-cases approach will be used for tabulations of data by visit (that is, involving only those subjects who attended each specific visit).

Categorical data will be summarised using the number and percentage of subjects in each category. Continuous data will be summarised using the mean, standard deviation (SD), median, 1st quartile, 3rd quartile, minimum, and maximum values.

#### 5.1.1 Missing values

Missing baseline values will not be imputed, meaning that such subjects will be excluded from analyses concerning change from baseline as this cannot be derived. Unless otherwise specified, the baseline value is defined as the latest pre-dose assessment.

Procedures for handling missing values that are not baseline values are included in the sections describing the individual analyses.

Analysis of PK parameters will only include samples that are available, i.e. missing values will not be imputed.

#### 5.1.2 Trial periods and date of permanent discontinuation of IMP

The treatment period will be defined as the time from exposure start to exposure end and the remaining time after exposure end will be defined as the safety follow-up period. SFU period is only applicable for subjects where last date of contact does not equal the date of exposure end.

Definition of date of permanent discontinuation of IMP, exposure start, and exposure end are given in [Panel 3](#).

THIS DOCUMENT CONTAINS CONFIDENTIAL INFORMATION AND MUST NOT BE COPIED OR MADE AVAILABLE TO ANY THIRD PARTY WITHOUT THE PRIOR WRITTEN CONSENT OF THE LEO PHARMA GROUP

### Panel 3: Date of permanent discontinuation of IMP, exposure start and end

Time point	Definition
Date of permanent discontinuation of IMP*	
 
Defined as the latest date of early termination visit (if existing) or date of onset of latest AE leading to withdrawal of IMP, otherwise date of the last visit, excluding SFU visit.
 

Exposure start	
 
Date and time of first dose.
 

Exposure end	
 
Date of Week 16 visit (if existing) at time 23:59:00, otherwise date of permanent discontinuation of IMP (if existing) at time 23:59:00, otherwise date of last IMP administration at time 23:59:00.
 

\*) Only defined for subjects who have a reason for permanent discontinuation of IMP recorded.

**Abbreviations:** AE = adverse event, IMP = investigational medicinal product, SFU=safety follow-up

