14.3.6 Estimand strategy

The primary endpoints will be analysed using a composite estimand strategy to handle the occurrence of two intercurrent events considered to affect the interpretation of the estimates of the endpoints:

- **Initiation of rescue treatment:** This event occurs when a subject initiates rescue treatment. This event can occur at the discretion of the investigator as described in Section 5.4. The timing of the event is defined as the date of initiation of the rescue treatment recorded in the eCRF.
- **Permanent discontinuation of IMP:** This event occurs when a subject is permanently withdrawn from treatment or the trial as described in Section 10.2.1. This event can occur at the subject's own initiative, at the discretion of the investigator or the sponsor as described in Section 10.2.1 or if the subject is lost to follow-up. The timing of the event is defined as the date of last IMP administration recorded in the eCRF.

The composite estimand evaluates the response rate without initiation of rescue treatment or permanent discontinuation of IMP. For subjects who received rescue treatment prior to Week 16 or who have permanently discontinued IMP prior to Week 16, observed data after the intercurrent events will be considered non-response, reflecting an assumption that initiation of rescue treatment or permanent discontinuation of IMP indicates either failure of the treatment to achieve response or that a possible positive response is not attributable to the treatment alone. Missing data for subjects who do not attend the Week 16 visit and where rescue medication has not been used, nor the subject has permanently discontinued IMP, will be imputed as non-response.

Binary efficacy endpoints will be analysed using the same estimand strategy as for the primary endpoints. The endpoints on successful self-injection will be analysed using the principles of estimands in ICH E9(R1) targeting the estimand attributes (population, variable, intercurrent event, and population-level summary) (37), while continuous efficacy endpoints will be presented as observed.

THIS DOCUMENT CONTAINS CONFIDENTIAL INFORMATION AND MUST NOT BE COPIED OR MADE AVAILABLE TO ANY THIRD PARTY WITHOUT THE PRIOR WRITTEN CONSENT OF THE LEO PHARMA GROUP

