#### 5.1.3 Treatment and trial completers

A subject who has not permanently discontinued IMP before Week 16 will be defined as a treatment completer.

A subject is considered to have completed the trial if they have completed all periods of the trial including the safety follow-up visit (Week 20).

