#### 5.3 Intercurrent events

Two intercurrent events are considered to affect the interpretation of the estimates of the endpoints:

- **Initiation of rescue treatment:** This event occurs when a subject initiates rescue treatment. This event can occur at the discretion of the investigator. The timing of the event is defined as the date of initiation of the rescue treatment recorded in the eCRF.

Rescue treatment will be defined by the following algorithm: Concomitant medications with 'Dermatitis atopic' or 'Dermatitis infected' as the preferred term for the indication and either of the following:

1. ATC2 code H02 or D07.
2. ATC4 code D11AH.
3. Preferred name:
  - delgocitinib,
  - crisaborole,
  - methotrexate,
  - ciclosporin,
  - azathioprine,

THIS DOCUMENT CONTAINS CONFIDENTIAL INFORMATION AND MUST NOT BE COPIED OR MADE AVAILABLE TO ANY THIRD PARTY WITHOUT THE PRIOR WRITTEN CONSENT OF THE LEO PHARMA GROUP

- mycophenolate-mofetil,
- mycophenolate-sodium,
- mycophenolate-acid,
- ruxolitinib,
- dupilumab,
- upadacitinib or
- abrocitinib

- **Permanent discontinuation of IMP:** This event occurs when a subject is permanently withdrawn from treatment or the trial. This event can occur at the subject's own initiative, at the discretion of the investigator or the sponsor, or if the subject is lost to follow-up.

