### 5.4.2 Primary analyses

The primary endpoints (IGA 0/1 at Week 16 and EASI75 at Week 16) will be analysed using the composite estimand strategy to handle the occurrence of intercurrent events (initiation of rescue medication or permanent discontinuation of IMP).

Missing data for subjects who do not attend the Week 16 visit and where rescue medication has not been used, nor the subject has permanently discontinued IMP, will be imputed as non-response.

The number and percentage of subjects achieving response will be presented together with the corresponding 95% CI.

The analysis will be based on the FAS.

THIS DOCUMENT CONTAINS CONFIDENTIAL INFORMATION AND MUST NOT BE COPIED OR MADE AVAILABLE TO ANY THIRD PARTY WITHOUT THE PRIOR WRITTEN CONSENT OF THE LEO PHARMA GROUP

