### Panel 11: Changes to the analyses described in the protocol

Section in CTP	Description of change	Brief rational
14.2 Trial analysis sets	The description of the full analysis set, and the safety analysis set has been updated such that subjects should both be assigned to treatment and dosed.	The definition in the CTP did not specify subjects to be assigned to treatment, but only dosed.
14.2 Trial analysis sets	In addition to the analysis sets defined in the CTP, an analysis set, called "usability analysis set ", for analysing endpoints related to IMP self-injection has been defined. Furthermore	The analysis set is described in the CTP, but not named. To ease readability and communication it has been defined and named usability analysis set
14.2 Trial analysis sets	A SFU analysis set is added to the list of the analyses sets	To analyse endpoints and assessments related to safety during the SFU period
14.3.16 General principles	In addition to what is stated in the CTP, the lower and upper quartiles will be used to summarise continuous data.	To align outputs with previous trials in the Tralokinumab project.
14.3.16 General principles	Baseline definition is added.	To define the baseline data.
14.3.16 General principles	It has been specified that the Wilson method is used to calculate the confidence interval for the responder analyses, and the statistically method Student's t-CI is used to calculate the CI for the continuous endpoints.	To specify what method is used.
14.3.6 Estimand strategy	Definition of date of permanent discontinuation of IMP has been changed to latest date of early termination visit (if existing) or date of onset of latest AE leading to withdrawal of IMP, otherwise date of the last visit, excluding safety follow-up visit rather than date of last IMP administration.	Definition in the CTP was erroneous.
14.3.3 Exposure and treatment compliance	From exposure start to end, not date of disc. of IMP. Presented both as continuous data and categorical.	End of exposure definition in CTP was erroneous.
14.3.7 Analysis of primary endpoints	Added a subgroup analysis for the primary endpoints (EASI75 at Week 16 and IGA 0/1 at Week 16). Each endpoint will be analysed by baseline IGA.	To look into subgroups.
14.3.4 Rescue medication	Definition of rescue medication has been updated to include upadacitinib and abrocitinib as preferred name.	The two treatments have been approved in the meantime.

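### The SAP re-dates permanent discontinuation to a visit date but still makes only data after that date non-response, so a recorded discontinuer's same-day score could count as a response

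*SAP*

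**What the plan says.** Protocol 14.3.6 fixes when permanent discontinuation happens: "The timing of the event is defined as the date of last IMP administration recorded in the eCRF". SAP Panel 3 gives a different date: "Defined as the latest date of early termination visit (if existing) or date of onset of latest AE leading to withdrawal of IMP". If neither exists, it is the last visit other than safety follow-up. A footnote limits the date to subjects who have a discontinuation reason recorded. Panel 11 enters this as a change to protocol 14.3.6, so it reaches the estimand as well as exposure. The only reason given is that the protocol definition was in error.

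The non-response rule in SAP 1.1 keeps the protocol's wording. For subjects who had rescue treatment before Week 16 "or who have permanently discontinued IMP prior to Week 16, observed data after the intercurrent events will be considered non-response". The same paragraph states the aim: "The composite estimand evaluates the response rate without initiation of rescue treatment or permanent discontinuation of IMP".

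SAP 5.3 dates rescue but gives no date for discontinuation, which it defines by occurrence: "This event occurs when a subject is permanently withdrawn from treatment or the trial". SAP 5.4.2 imputes missing Week 16 data only for subjects without an event: "where rescue medication has not been used, nor the subject has permanently discontinued IMP, will be imputed as non-response".

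SAP 5.1.4 lets early termination data stand in for a missing scheduled visit within a window around the target day. SAP 5.5.2 applies the primary-endpoint strategy to the by-visit responder tables.

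**The concern.** Under the protocol's date, every score after the last dose of a discontinuer is after the event and is non-response. Under two of Panel 3's branches (early termination visit, last visit) the event date is itself a visit date on which IGA and EASI may be scored. A score on that day is on the event date, not after it, and the rule in SAP 1.1 does not catch it.

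No other text settles the same-day case for discontinuation. The only same-day rule is in protocol 14.3.4. It concerns rescue, and it keeps the score. A programmer working by analogy would also keep the discontinuer's score.

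The response rates are the primary result of this single-arm trial, and they are also reported separately for adults and adolescents. A responder who had stopped treatment would contradict the stated estimand, and at Week 16 the error runs in one direction only.

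**Working it through.** **Inputs.** N = 130, of whom about 30 are adolescents; assumed response rates 19% (IGA 0/1) and 29% (EASI75) (protocol 14.1). Visit windows: Day 7x − 6 to 7x + 7 for Week x (SAP Panel 4). The end-of-treatment form asks whether IMP was stopped before Week 14 and, if so, why (protocol 11.8).

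**1. The plan's precision figures reproduce.** SE = √(p(1−p)/n); half-width = 1.96 × SE.
- IGA 0/1: √(0.19 × 0.81/130) = 3.44%; half-width 6.74 points.
- EASI75: √(0.29 × 0.71/130) = 3.98%; half-width 7.80 points.

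**2. The two dates applied to example subjects.** All are recorded discontinuers. *After* is read as score day > event day.

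| Example | Protocol date | Panel 3 date | Score day | Protocol date, *after* | Panel 3 date, *after* | Panel 3 date, *on or after* |
|---|---|---|---|---|---|---|
| A: last dose Day 84, early termination visit Day 108 | 84 | 108 | 108 | non-response | score kept | non-response |
| B: last dose Day 84, no early termination visit, no AE leading to withdrawal, last visit is Week 16 | 84 | 112 | 112 | non-response | score kept | non-response |
| C: last dose Day 84, AE onset Day 90, no early termination visit | 84 | 90 | 112 | non-response | non-response | non-response |
| D: last dose Day 70, AE onset Day 60, no early termination visit | 70 | 60 | 112 | non-response | non-response | non-response |
| E: last dose Day 84, AE onset Day 90, early termination visit Day 108 | 84 | 108 | 108 | non-response | score kept | non-response |

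The gap comes from the two branches that put the date on a visit. AE onset alone does not cause it unless onset falls on the scoring day.

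**3. Direction at Week 16.** The window is Day 106 (7 × 16 − 6) to Day 119 (7 × 16 + 7). A subject with a recorded reason stopped before Week 14 (Day 98), so under the protocol's date any score in that window is non-response. The literal Panel 3 rule can therefore only turn a non-response into a response.

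**4. How a subject gets there.** The early termination visit must fall in Day 106–119. That is 22–35 days after a Week 12 dose (Day 84), 36–49 days after a Week 10 dose (Day 70), and longer after earlier doses. The other route is example B.

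**5. Size per affected subject.**
- Total: 1/130 = 0.77 points. As a share of the half-width: 0.769/6.74 = 11% (IGA 0/1) and 0.769/7.80 = 10% (EASI75).
- Adults, 130 − 30 = about 100: 1/100 = 1.0 point.
- Adolescents, about 30: 1/30 = 3.3 points, against a half-width of 1.96 × √(0.19 × 0.81/30) = 14.0 points (24%).

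The number affected, k, is an assumption. For k = 1 to 5 at N = 130 the shift is 0.77 to 3.85 points. With the SAP's Wilson limits, IGA 0/1 moves from 25/130 (19.2%, 13.4 to 26.9) to 26/130 (20.0%, 14.0 to 27.7) at k = 1, and to 30/130 (23.1%, 16.7 to 31.0) at k = 5. A shift of one full half-width would need 6.74/0.769 = 8.8, so 9 subjects for IGA 0/1, or 7.80/0.769 = 10.1, so 11 for EASI75.

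**6. By-visit tables.** The direction is mixed.
- Up: an early termination visit 8–21 days after a Week 2 dose (Day 14) falls in the Week 4 window (Day 22–35). The same lag after a Week 10 dose (Day 70) falls in the Week 12 window (Day 78–91). Either score sits on its own event date.
- Down: AE onset Day 80, last dose and Week 12 score both on Day 84, no early termination visit. Under the protocol's date the score is kept. Under Panel 3 (Day 80) it is after the event and becomes non-response.

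**The case against.** The strongest reply is that the SAP already means a status rule. The estimand sentence in 1.1, the event definition in 5.3 and the imputation sentence in 5.4.2 all fit the reading that any discontinuer is a non-responder, whatever the date. SAP 1 also sends derivation rules to the reviewer's guide and define.xml, which are not available here and may contain such a flag. This stands as to intent. It does not remove the conflict: the SAP states a date, ties it to the estimand, keeps the word *after*, and does not say which governs.

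The second reply is rarity, and it stands. Protocol 10.3 asks for the early termination visit as soon as possible after the last dose and asks discontinuers for no later Week 16 visit. Both Week 16 routes therefore depart from the expected follow-up, and the subject must also meet the response criterion. It is not explicit that SAP 5.1.4, which speaks of data summaries, reaches the primary analysis. The extracted schedule does not show with certainty that IGA and EASI are scored at early termination.

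A reader might go further and infer that, because the Panel 3 date can fall at or after Week 16, such a subject fails the condition of having discontinued before Week 16 and becomes a completer under SAP 5.1.3: "A subject who has not permanently discontinued IMP before Week 16 will be defined as a treatment completer". The documents do not support this. The form records a reason only for a stop before Week 14, and only subjects with a recorded reason have a Panel 3 date. All of them discontinued before Week 16, and 5.1.3 does not refer to the Panel 3 date.

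**Conclusion.** The point holds as a conflict inside the SAP: the Panel 3 date combined with the *after* wording gives a result contrary to the stated estimand for a score taken on the event date. It does not show that the sponsor chose to count discontinuers as responders. Nor can one infer that the new date raises response rates everywhere: that holds at Week 16, while in the by-visit tables an AE onset before the last dose can lower the rate.

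The size is 0.77 points per affected subject in the total cohort, about 1.0 in adults and 3.3 in adolescents. The number affected is unknown and probably small at Week 16. The estimate rests on literal application of the date rule, on IGA and EASI being scored at the early termination visit and, for that route, on SAP 5.1.4 reaching the responder analyses. No formal test is planned, so no decision threshold is at stake, and the precision figures in protocol 14.1 are unaffected. Severity is minor to should-fix: the effect is likely small, but the rule is wrong as written and nearly free to correct.

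**What to change.** In SAP 5.4.2, state that any subject with a recorded permanent discontinuation of IMP before Week 16 is a non-responder at Week 16, regardless of the Panel 3 date and of any early termination, unscheduled or Week 16 data. The end-of-treatment form asks only about stops before Week 14, while SAP 5.3 also counts withdrawal from the trial. The sentence should therefore also say how a subject who took the Week 14 dose and then withdrew is handled.

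For the by-visit tables in SAP 5.5.2, do one of two things:
- make scores on or after the discontinuation date non-response; or
- return to the protocol's last-dose date for the estimand and keep the Panel 3 date for exposure only.

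Both close the same-day gap but they are not equivalent. In the example with AE onset on Day 80 and last dose and score on Day 84, the first gives non-response and the second keeps the score. The SAP should name its choice and log it in Panel 11.

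The cost is a few sentences and a few programming lines before database lock, using a record already collected. The downside is a slightly lower reported response rate if any such subjects exist.
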